4.4. Protections Against Risks

In order to preserve privacy and protect the confidentiality of participants, a series of security procedures will be undertaken. IRB and HIPAA regulations concerning confidentiality will be strictly enforced. All study personnel receive training and certification in human subjects protection and HIPAA regulations. Each study participant will be given a unique numeric identifier upon study entry. Names and other protected health information will not be stored in the same database as survey and medical information. All computers used for research purposes adhere to the institution's requirements regarding password protection, data encryption, anti-virus protection, and intrusion detection. All Internet-based data communications are encrypted. All hard copy study-related materials and data will be stored in locked file cabinets in secure locations. The research team has never previously experienced a breach of participant confidentiality in a research study.

5. Data Handling and Statistical Analysis

All patients' shadow files/research records that are housed at Rutgers will be maintained on a secure server at Rutgers CINJ. Hard copies of all files will be stored in locked file cabinets on the 5th floor of CINJ in Population Science department and will be retained until ten years after the last publication. Audiotapes of any feedback or usability interviews will be collected and will be labeled with the study ID#, no names will be included. Electronic copies of audio files will be stored on the secure hard drive, hard copies will be stored in a locked cabinet in the Population Science department. All audio files will be handled as described in the Policy and Procedure,

entitled Data Storage Management and Transfer of Audio and Video Research Data and will be retained until ten years after the last publication.

Research transcripts and data will be maintained on secure servers with restricted authorization for research team members only and will be destroyed ten years after the last manuscript has been published. The PI and the designated research team will retain the data keys that link patient names with their unique identifiers for 10 years. The retention of accurately recorded and retrievable research data is necessary in order to ensure scientific integrity. Research records will include sufficient detail to permit examination for the purpose of replicating the research, responding to questions that may result from unintentional error or misinterpretation, establishing authenticity of the records, and confirming the validity of the conclusions.

Databases for participant recruitment and tracking, medical records review data, and participant survey data will be developed and maintained by the CINJ Population Science Research Support Core using HIPAA-compliant DatStat software. Approval for use of this software in research studies has been provided by the Rutgers Biomedical and Health Sciences Institutional Review Board (IRB). (The approval process included: obtaining a Technology Professional Service Agreement and a Business Associate Agreement from DatStat; the approval of a Security Questionnaire from the Rutgers Office of Information Technology; and the completion of a Security Risk and Assessment Tool by the Rutgers CINJ Office of Information Technology.) The software allows for research study personnel to be assigned data access and privileges specific to their role on the study. Online surveys will be completed by participants using a secure website (hosted on DatStat servers) developed and maintained by the CINJ Population Science Research Support Core.

DatStat secure servers are registered with site certificates provided by AddTrust that provide for advanced encryption over the wire. As each user moves through the survey form, his/her responses are encrypted while in-transit between the browser and DatStat's server using SSL (Secure Sockets Layer) and 40, 56, or 128-bit Public Key Encryption. All servers used for data collection are highly fault-tolerant and equipped with redundant, hot-pluggable power supplies, redundant network interfaces, and RAID 5 hot-swappable disk storage. All primary servers are plugged into a monitored, uninterruptible power supply (UPS). DatStat servers are stored in a locked server cabinet/rack, which are housed in a state-of-the-art, well-ventilated data center. Physical access to servers and data backup is restricted to a minimal number of information technology professionals. The servers are secured with physical and firewall security.

5.1. Primary Aim: Is the intervention trial feasible?

Approach and Analysis

For feasibility, 2 questions will be addressed: 1) Are patients joining/staying in the trial? We judge this study feasible if the participation rate (consented and complete baseline) is equal to or greater than 70% and the retention rate at follow-up is 85%. These "yardsticks" were selected to ensure there is sufficient interest to proceed to a larger scale trial. 2) Are participants using the DA in the way that was intended? We will evaluate log-ins, pages viewed, and how long modules are viewed. If participants review more than 75% of the pages, we will consider this acceptable usage. To evaluate the acceptability, we will

examine: whether participants use the DA, to what degree they use it, and factors predicting uptake and use. We will also look at whether patients 1) opened the web aid and 2) viewed each page. First, basic descriptive information will be gathered regarding participant log-ins and number and duration of log-ins. Second, DA evaluation and User Interface Satisfaction surveys will be examined.

We will judge the DA as acceptable if 75% of participants used it and if the average score was > 5.6/7 on the DA evaluation. *Using regression analyses, we will examine the following for association with DA use: younger age, internet familiarity, and higher education. The small sample (N = 40) and limited range of correlate categories limits options for statistical analyses. Missing values will be imputed from observed information (SAS Procedures MI and MIANALYZE). Confidence intervals and inferential procedures will adjust for uncertainty due to imputation.*

Table 1. Probability of declaring feasibility under various assumptions

Feasibility Component	Unaccept-able Rate	Acceptable Rate	Decision rule for claiming Feasibility	Prob. Declare Feasible under Unacceptable Rates	Prob. Declare Feasible under Acceptable Rates
Acceptance Rate	65%	70%	If 80 women recruited by the 114th (inclusive) approached	5%	96%
Completion Rate	79%	85%	If 68 participants complete survey	5%	96%

Power. We expect to approach a maximum of 140 to enroll 100 women. If 100 women are enrolled in the study by the 140th patient approached and 85/100 participants complete the survey, then we will declare the study feasible. We chose the sample size and decision rules so that the probability of declaring feasibility would be approximately 5% under unacceptable rates of acceptance and completion and exceed 95% under acceptable rates. Power calculations are in **Table 1**. If the true acceptance and completion rates are 65% and 79%, respectively, which we consider to be too low to warrant further research, then the probability of declaring feasibility would be 5%. If the true acceptance and completion rates are 70% and 85%, respectively, which we consider large enough to warrant further research, then the probability of declaring feasibility would be 96%. These figures are based on binomial distributions

5.2. Secondary Aim 2: What is the impact of DA on CPM knowledge, psychosocial factors, decisional conflict, completeness of preparation, and CPM intention?

Approach and Analysis. Our outcomes are knowledge, perceived risk for recurrence, cancer worry, coping efficacy, anxiety, decisional conflict, preparedness, and intention. We anticipate that 100 women will complete the baseline and 85 will complete the follow-up. We will characterize the data using standard methods (means, medians, standard deviations, 95% confidence intervals) for the sample and separately by study arm. In exploratory analyses, we will use two sample repeated measures to compare outcomes using an intent-to-treat approach. We will assess associations among the outcome variables using Pearson's correlation coefficients. We will also characterize the patterns of missing data.

6. Reporting Results

The policies and procedures of Rutgers University's legal department (see: Investigator's Handbook) will govern publication of the results of this trial. The results of this trial will be submitted for publication in a timely manner following its conclusion. The Rutgers Cancer

Institute of New Jersey PI and all co-authors will review any abstract of manuscript prior to its submission.

7. Bibliography

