3.2.3. Sample Size for RCT. We anticipate we will recruit participants for about 6months (months 17-22). Our goal is to enroll 90 to 130 women (65 in UC and 65 in CPM DA). We are anticipating a 70-75% acceptance rate based on our BRDA study. To obtain $N = 130$ (90 MSKCC, 10 CINJ, 30 MGH), we estimate approaching 169-182 women. Because acceptance rates are a study goal, this is only an estimate, and thus we allow 6-12 months for accrual.

3.2.4 Usual Care. Usual care consists of what traditionally occurs at both sites. At both sites, the surgical oncologist educates WSC regarding the facts about CPM, including the fact that it is not medically indicated, and does not reduce the risk of the spread of cancer. If interested, the patient is referred to a plastic surgeon.

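### The completion half of the feasibility rule is written for 80 or 100 women while 90 to 130 are planned, and the plan does not say whether its 85% rate or its counts govern

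*Combined protocol and SAP*

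**What the plan says.** Section 3.2.3 sets the trial size: "Our goal is to enroll 90 to 130 women (65 in UC and 65 in CPM DA").

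Section 5.1 then states the completion criterion in three ways.
- As a rate: the study is feasible if participation is at least 70% and "the retention rate at follow-up is 85" per cent.
- As a count in Table 1's decision-rule column: "If 68 participants complete survey". The row gives no denominator. The acceptance row above it reads "If 80 women recruited by the 114th (inclusive) approached".
- As a fraction in the Power paragraph: "We expect to approach a maximum of 140 to enroll 100 women", with feasibility declared under the condition "If 100 women are enrolled in the study by the 140th patient approached and 85/100 participants complete the survey". This paragraph sends the reader to Table 1 for its calculations, although Table 1 uses other numbers.

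Table 1 gives the completion rule a 5% chance of passing at a true rate of 79% (unacceptable) and 96% at 85% (acceptable).

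Other sizes appear nearby. Section 5.2 says "We anticipate that 100 women will complete the baseline and 85 will complete the follow-up", and the paragraph on predictors of decision-aid use says "The small sample (N = 40").

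**The concern.** Completion is one of the two components of the primary feasibility verdict, which is meant to inform whether a larger trial should follow. A count tests a retention rate only if its denominator is fixed. The count 68 corresponds to 85% of 80 women, and 85 corresponds to 85% of 100. The plan now allows any enrolment from 90 to 130. It gives no completion count and no operating characteristics for 90 or 130, and it does not restrict the rule to the first 80 or first 100 women. Someone judging feasibility at the end could apply the rate or a count and reach opposite conclusions, and could make that choice after seeing the data.

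**Working it through.** **Inputs.** Enrolment 90 to 130 (section 3.2.3). Counts 68 (Table 1) and 85/100 (Power paragraph). Retention yardstick 85% (section 5.1). Unacceptable and acceptable completion rates 79% and 85% (Table 1 and Power paragraph). Binomial distribution, as the Power paragraph states.

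**Formula.** With n enrolled, r completers required and true completion rate p, P(pass) = Σ over x = r to n of C(n, x) pˣ (1 − p)ⁿ⁻ˣ. The implied retention is r/n.

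**The plan's own figures.** At the sizes the counts fit, 68 of 80 gives 11.6% at a true 79% and 57.6% at a true 85%; 85 of 100 gives 8.5% and 56.8%. The stated 5% and 96% are not reproduced. Strict inequality, normal approximations, the joint probability of both components (assuming independence) and a search over other n also failed to give 5% and 96% together.

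**Planned sizes.**

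| Enrolled n | Required r | r/n | P(pass) at 79% | P(pass) at 85% |
|---|---|---|---|---|
| 90 | 68 | 75.6% | 82.5% | 99.4% |
| 100 | 68 | 68.0% | 99.7% | about 100% |
| 130 | 68 | 52.3% | about 100% | about 100% |
| 130 | 85, read as a count | 65.4% | 99.99% | about 100% |
| 90 | 77 (85% rate) | 85.6% | 7.7% | 51.4% |
| 130 | 111 (85% rate) | 85.4% | 4.2% | 51.2% |

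The 85% thresholds are 0.85 × 90 = 76.5, rounded up to 77, and 0.85 × 130 = 110.5, rounded up to 111. At 90 enrolled, the Power paragraph's condition of 100 enrolled cannot be met.

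**Opposite verdicts.** With 98 of 130 completing, retention is 98/130 = 75.4%. That is below 85%, so the rate fails, but 98 exceeds both 68 and 85.

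The probability of such a conflict is the difference between two tails. At 130 enrolled and a true 79%, a count of 85 passes while the rate fails with probability 0.9999 − 0.0423 = 0.958. At 90 enrolled and a true 79%, the count of 68 passes while the rate fails with probability 0.825 − 0.077 = 0.748. At 130 and a true 85%, the conflict with a count of 85 has probability about 1 − 0.512 = 0.488.

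**The case against.** The strongest reply is that section 5.1 opens with the criterion as a proportion. A rate of 85% scales with any enrolment, and the other two statements resolve to the same 85% at their own sizes: 68 beside 80 recruited, and 85 written over 100. On this reading the counts merely illustrate the rate. That much stands: the plan does contain a rule that works at any size. What it lacks is a statement that this rule prevails. The column holding 68 is the one that sets out the decision rules, and the Power paragraph attaches the declaration of feasibility to 100 enrolled and 85/100.

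Some stronger readings go beyond the documents.
- A reader might infer that one count can mean anything from 52% to 94% retention. None does: 68 runs from 52.3% (of 130) to 75.6% (of 90). A figure of 94.4% arises only by applying 85 to 90 women, and the plan writes 85 over 100.
- A reader might infer that the counts pass or fail almost any retention. The calculations support that only near the rates the plan names. A count of 85 among 130 would still fail if retention were well below 65%.
- A reader might infer that 68 and 85 survive from superseded designs, or that 40 is half of 80 and so one arm. Both are plausible, but the plan gives no design history and does not say what the 40 counts.
- A reader might infer that the open range lets recruitment stop when the acceptance rate looks good. The plan describes no such practice.

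**Conclusion.** The point stands as a conflict within the primary decision rule. The three statements of the completion criterion agree only at particular sizes (the rate and 68 at 80 women, the rate and 85 at 100), none is named as governing, and they can reverse the verdict at the planned sizes. Applied as written, Table 1's 68 would pass the unacceptable 79% rate with probability 83% at 90 women and about 100% at 130, against the stated 5%. Read as a count, 85 would pass it with probability above 99.9% at 130.

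These figures assume independent completions with a common rate, as the plan's binomial basis implies. The results for 85 at 130 also assume that it is taken as a count rather than as a fraction of 100.

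Making the rate the sole rule removes the dependence on enrolment. It does not restore 5% and 96%: at a true 85%, an 85% threshold passes only about half the time at any of these sizes.

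**What to change.** 1. In section 5.1, state one completion rule: at least 85% of all randomised women. That is 77 of 90, 85 of 100 or 111 of 130. Delete the stand-alone counts from Table 1 and the Power paragraph, and name the follow-up survey that counts as completion.
2. Name one enrolment number at which feasibility is judged.
3. Recompute Table 1 at that number and restate its figures in the Power paragraph. For completion, the pass probability is 7.7% (N = 90) or 4.2% (N = 130) at a true 79%, and about 51% at a true 85%.
4. Align the N = 40 in section 5.1 and the 100 and 85 in section 5.2 with the chosen size. If the 40 is meant as the decision-aid arm, equal allocation gives 45 to 65.

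The cost is a protocol amendment to wording and one recomputed table, with no extra patients. The downside is that the stated operating characteristics become clearly less favourable. Keeping 79% against 85% with an error of at most 5% and a pass probability of at least 95% would need about 446 women (threshold 367). The sponsor should therefore either accept the weaker figures openly or reconsider the pair of rates.

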The Layout of the DA is as planned: **Module 1** (2 minutes) contains an orientation/tutorial program which describes the DA, how to navigate it, and provides basic training. **Module 2** (5 minutes) is a risk education module that addresses perceptions and facts about contralateral BC risk. **Module 3** (5 minutes) presents medical facts about with CPM. The section will be guided by questions including: "What does a reconstructed breast look like?" "Is there a difference in recovery time if I choose CPM?" and "Are there more complications possible if I choose CPM?" Participants can select not to view graphic illustrations. **Module 4** (10 minutes) is an anxiety assessment and self-efficacy enhancement tool. Because anxiety about recurrence in the other breast is a primary motivator for CPM, this module addresses that anxiety. Patients will rate the degree of worry about recurrence in the other breast and metastatic disease and their confidence in coping with these worries and then will be offered coping strategies. A patient video will accompany with each strategy. We will use the fear of recurrence session materials from our ongoing grant for women with gynecological cancer as a guide. **Module 5** (10-15 minutes) contains personal narratives from women who chose or did not choose CPM. Patients from CINJ will be interviewed by [name]. Women will discuss the process they went through to make the decision, including values and preferences they weighed, and other concerns they had. Four clips will be selected that provide balanced information regarding satisfaction with the decision and possible complications. **Module 6** (10 minutes). is the interactive decision section which guides participants through the advantages and disadvantages of CPM. The participant will rank and weigh motivations, consider others' opinions, and assess assistance they might want. The final screen will summarize responses. It will not specifically endorse a decision, but rather will encourage women to discuss relevant options/contraindications of CPM with their surgeon, family, and friends.

PHASE 1, Step 3, Usability Testing, Iterative feedback, and Final Alterations, Months 14-16. Step 3 will be devoted to obtaining feedback about our interactive web-based prototype and making final modifications to the intervention and programming.

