3.2. Phase 2: CPM-DA FEASIBILITY TRIAL (Months 17-24)

The primary goal is to evaluate whether women will participate, use the DA, and evaluate the DA positively. A second goal is to gather pilot information about the impact of the DA on knowledge, psychological constructs, decisional conflict, and preparedness. We will conduct a small randomized trial assigning patients to receive Usual Care or the CPM-DA.

3.2.1. Phase 2 Inclusion criteria:

1. Completed initial surgical consult with breast cancer surgeon at CINJ/MGH/MSKCC and is considering CPM, regardless of the surgical treatment of their primary breast cancer (lumpectomy/mastectomy).
2. Has home internet access.
3. Has a first, primary diagnosis of unilateral Stage 0, 1, 2, or 3a breast cancer or Stage 1-3b who is down-staged to Stage1-3a with neo-adjuvant chemotherapy
4. ≥ 18 years
5. Speaks and reads English
6. WSC [does not have hereditary breast/ovarian cancer syndrome (BRCA carrier, strong family history)]. If there is any uncertainty, the surgeon will use the Tyrer-Cuzick (Tyrer et al., 2004) risk model to calculate risk. For this study, anyone with a lifetime risk up to 19% on the Tyrer-Cuzick model will be considered average risk for breast cancer. Anyone with a lifetime risk of 20% or greater will be excluded from participation.
7. Able to provide meaningful informed consent.

3.2.2. Phase 2 Participant Recruitment and Consent Procedures. Staff will identify women scheduled for a surgical consultation. Because this study targets women considering CPM, participants will be approached after the consult as the surgeon discusses options the patient is eligible for at this time. The surgeon will refer the patient if she is considering CPM. The project coordinator or designated study staff will review eligibility with the surgeon and medical staff, and, if the patient meets eligibility, provide an explanation of the study and cover all of the aspects of the consent with the patient.

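### Use of the decision aid is one of section 5.1's two feasibility questions, but the rule that declares feasibility contains only acceptance and completion, and nothing says how a failed use verdict would count.

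*Combined protocol and SAP*

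**What the plan says.** All references are to the combined protocol and SAP.

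- **Opening section, Primary Aim.** Feasibility is defined by acceptance and participation. DA use is not mentioned there.
- **Section 3.2.** "The primary goal is to evaluate whether women will participate, use the DA, and evaluate the DA positively".
- **Section 5.1, framing.** "For feasibility, 2 questions will be addressed: 1) Are patients joining/staying in the trial", followed by "2) Are participants using the DA in the way that was intended".
- **Section 5.1, feasibility judgement.** "We judge this study feasible if the participation rate (consented and complete baseline) is equal to or greater than 70"% and retention at follow-up is 85%. The stated purpose of these two yardsticks is to show enough interest for a larger trial.
- **Section 5.1, use.** "If participants review more than 75% of the pages, we will consider this acceptable usage". Separately, the DA is judged acceptable if 75% of participants used it and its mean evaluation score is above 5.6 out of 7.
- **Section 5.1, feasibility Table 1.** There are two rows, acceptance (80 recruited by the 114th approached) and completion (68 complete).
- **Section 5.1, Power.** If 100 women are enrolled by the 140th approached and 85 of the 100 complete the survey, "then we will declare the study feasible". The rates called high enough to justify further research are acceptance 70% and completion 85%.

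**The concern.** The plan asks two questions under feasibility, but only the first can change the answer. Question 2 has thresholds of its own, yet they lead to different labels (acceptable usage, acceptable DA), and no sentence links those labels to the declaration or to the decision on a larger trial. The language about going forward attaches only to acceptance and completion.

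For a web aid that women use on their own, uptake is a central uncertainty. If use turns out low, the team would hold a feasible trial and an unacceptable aid with no pre-stated way to combine the two verdicts. The choice would then be made after the logs have been seen.

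**Working it through.** **1. Terms in each version of the rule**

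| Place | Acceptance | Completion or retention | DA use |
|---|---|---|---|
| Primary Aim, opening section | yes | participation | no |
| Section 3.2, primary goal | yes | not stated | yes |
| Section 5.1, two questions | yes | yes | yes |
| Section 5.1, judgement | 70% | 85% | no |
| Section 5.1, Table 1 | 80 by 114 | 68 complete | no |
| Section 5.1, Power | 100 by 140 | 85 of 100 | no |

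None of the three operative rules has a use term. Followed literally, each gives the same probability of declaring feasibility whether no woman or every woman in the DA arm opens the aid.

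**2. The plan's own figures: 5% and 96%**

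The plan says these are binomial, so P(X >= r) = sum over k = r..n of C(n,k) p^k (1-p)^(n-k). Unacceptable rates are 65% (acceptance) and 79% (completion); acceptable rates are 70% and 85%. For the Table 1 completion row the denominator is taken to be the 80 recruited.

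| Rule | Unacceptable rate | Acceptable rate |
|---|---|---|
| 80 of 114 accept | 0.144 | 0.530 |
| 68 of 80 complete | 0.116 | 0.576 |
| Joint, Table 1 rule | 0.144 x 0.116 = 0.017 | 0.530 x 0.576 = 0.305 |
| 100 of 140 accept | 0.064 | 0.395 |
| 85 of 100 complete | 0.085 | 0.568 |
| Joint, Power rule | 0.064 x 0.085 = 0.005 | 0.395 x 0.568 = 0.225 |

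The 96% does not reproduce for either row or jointly, and shifting the cut-offs by one does not recover it.

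**3. What a use condition would do**

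Take the plan's existing criterion, 75% used it, applied to the DA arm: r = 0.75n rounded up. The arm sizes are 40 (half of 80 in Table 1), 50 (half of 100 in the Power text) and 65 (section 3.2.3). The true use rates are assumptions. The ends, 63% and 86%, are the range for use and adherence that the background section gives for other web interventions; 80% is the share who logged in to the team's earlier reconstruction aid.

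| DA arm | Users needed | 63% | 70% | 80% | 86% |
|---|---|---|---|---|---|
| 40 | 30 | 0.077 | 0.309 | 0.839 | 0.981 |
| 50 | 38 | 0.037 | 0.223 | 0.814 | 0.982 |
| 65 | 49 | 0.024 | 0.210 | 0.860 | 0.993 |

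**4. Three-part rule at 70% acceptance, 85% completion and 80% use**

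This assumes that use is independent of the other two parts.

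- Table 1 rule, 40 in the DA arm: 0.305 x 0.839 = 0.256.
- Power rule, 50 in the DA arm: 0.225 x 0.814 = 0.183.

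**The case against.** The best defence is that the rule follows the plan's own definition. The Primary Aim defines feasibility as acceptance and participation, and the opening section names acceptability, feasibility and preliminary efficacy as separate targets. On that view use belongs to acceptability, where it has pre-stated thresholds, and separate verdicts are a legitimate design. This stands in part. Use is left out of the declaration but not out of the plan: at very low use the aid would fail both the page criterion and the acceptability criterion. It does not remove the conflict with section 3.2 and with the two-question framing in 5.1, nor does it say how the verdicts combine.

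Three stronger readings are tempting and should not be drawn.

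- A reader might infer that the larger trial would go ahead whatever the uptake. No section says that; the plan is silent on what follows from a feasible trial with an unacceptable aid.
- A reader might see the two 75% figures as contradictory. One concerns depth (pages reviewed) and the other uptake (share of women who used the aid). They can coexist, although the plan does not define what counts as having used it.
- A reader might infer that the page threshold penalises intended behaviour, because in Module 3 "Participants can select not to view graphic illustrations". The text speaks of illustrations, not pages. No page counts are given, and nothing says that opting out lowers the count of pages viewed.

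It is also fair to say that a third condition makes success harder to declare.

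**Conclusion.** The point holds in this limited form: the declaration omits a component that sections 3.2 and 5.1 place within the primary goal, so feasibility could be declared while the plan's own use criteria fail, and no rule reconciles the two outcomes. This rests on reading the sections side by side and needs no assumption.

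The size of the remedy does rest on assumptions: equal arms, 40 to 65 women on the DA, a simple used or not-used outcome, and a true use rate somewhere in 63-86%. Under these a 75% condition passes about 2-8% of the time at the low end and 98-99% at the high end, so it separates poor from good uptake at sizes already planned. These figures do not apply to a stricter definition, such as a minimum share of pages per woman, for which the documents give no rate.

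Separately, the existing rule gives about 22-31% under the acceptable rates, not 96%. Table 1 therefore needs recomputing whether or not use is added.

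**What to change.** 1. In the Power paragraph of section 5.1, make the declaration also require the plan's existing criterion that 75% used the DA. The denominator is all women randomised to the DA, the source is the web logs, and a woman who never logged in counts as not used. State what counts as use.
2. Add a Use row to the feasibility Table 1, with its unacceptable and acceptable rates and the DA-arm denominator.
3. Recompute all rows and restate the joint probabilities of declaring feasibility, using one sample size throughout.
4. Align the Primary Aim in the opening section, section 3.2 and both parts of section 5.1 on what feasibility includes. State what the remaining verdicts (page depth and the mean evaluation score) contribute to the decision on a larger trial.

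If the sponsor prefers to keep use as a separate acceptability endpoint, the alternative is to say so in all these places and give that endpoint an explicit go/no-go role.

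No new data are needed, because log-ins and page views are already to be collected. The cost is revised text, a recalculated table and a lower stated chance of declaring feasibility: about 18-26% at 70% acceptance, 85% completion and 80% use, compared with 22-31% for the two-part rule. If that is too low, the cut-offs or the sample size must be reconsidered, and the two-part rule already calls for that.
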